Suicide Prevention for Patients With Chronic Pain

NCT04490265

10/30/2020

Title: Suicide Prevention for Patients with Chronic Pain

Specific Aims/Purpose: The goal of the current proposal is to ensure Problem-solving Treatment (PST) is remediating problem-solving deficits for Veterans with chronic pain and moderate suicide risk. Veterans with chronic pain and moderate suicide risk (n=60) will be randomized to receive remote-PST or remote-attentional control. We will assess problem-solving deficits through self-report, objective neuropsychological assessment and the report of the Veteran's support person (e.g., significant other, caregiver, spouse, partner, family member, friend).

Hypothesis:

Aim 1: Estimate the effect of remote-delivered PST on targets. We hypothesize that PST reduces our primary target, problem-solving deficits as assessed through (H1) self-report, (H2) objective neuropsychological assessment, (H3) caregiver report, as compared to attentional control. We hypothesize that PST reduces our secondary targets (H4) feelings of burdensomeness,²⁵ and (H5) feelings of not belonging²⁵, as compared to attentional control.

[figure not shown]
Exploratory Aim 2: Explore the effect size of PST as compared to attentional control on suicide outcomes including: (H6) intensity of suicidal ideation,²⁶ (H7) difficulties coping with suicidal ideation²⁷ and chronic pain outcomes (including (H8) chronic pain²⁸⁻³⁰ and (H9) pain-related disability³¹).

Scientific Rationale and Significance: Every day, 120 people die from suicide – that is one person every 15 minutes.¹ Suicide prevention treatments focus on those at highest risk and are primarily delivered as mental health treatments,²⁻⁵ and yet 70% of patients with suicide risk do not attend mental health treatment.⁶ Developing treatment for patients not served by existing suicide prevention programs will improve access to care and is necessary to stop suicide.

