When a participant is withdrawn from the research for safety concerns, our team will retain clinical responsibility until continuing care is successfully transferred to the appropriate provider (e.g., emergency department, hospitalization, psychiatrist, local suicide prevention coordinator, primary care provider). The following situations will necessitate participant withdrawal from the research (but not clinical care):

- Suicide attempt
- Indication that participant has developed definite intent to carry out a suicide plan, as measured by endorsement of item 5 on Section I of the C-SSRS.
- In addition, if there is a significant increase in the severity of suicidal ideation the participant will be reviewed by an internal study safety team comprised of 3 study investigators to determine appropriateness for continued participation. Increased risk will include an increase of 2 points on the C-SSRS from a participant's baseline level (e.g., moving from a baseline C-SSRS score of 2 [i.e., thoughts of killing oneself without any associated method or intent] to a C-SSRS score of 4 [i.e., suicidal thoughts with some, limited intent to act on them]).

Data Analysis Plan: We will explore the data using scatterplot graphs and calculating the means, standard deviations, proportions, histograms, etc. to explore the distributions of the data, identify outliers and calculate correlations between variables. We will calculate the percent change from baseline for each measure. We will also calculate the effect size (Cohen's D) for the change in each arm from pre to post treatment and calculate the effect size of the change in treatment between arms. Consistent with best practices for preliminary data analysis, we will not calculate statistical significance as we are not be powered to find an effect.^{90,91} The analyses will be conducted with intent to treat approach.

Best practices for determining improvement in executive functioning include using self-report, objective and support person report. While it is not expected all measures will show improvement due to variability in the assessment approaches, there should be an indication of clinically significant improvement across multiple assessments. Our preliminary data is consistent with previous research that finds PST has a moderate effect on self-report of problem-solving deficits (Cohen's D >0.22)^{45,46} as

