compared to control and a small effect on objective measures of problem-solving deficits (Cohen's $D > 0.15$) as compared to control - and these are clinically significant.

We will conclude that our trial shows support for target engagement if we find a clinically significant effect size for PST as compared to control for two of the three domains (self-report Cohen's $D > .22$; objective neuropsychological tests Cohen's $D > .15$ for at least two measures; support person report Cohen's $D > .22$) and no domain showing support for control over PST (self-report Cohen's $D > .22$ in support of control; objective neuropsychological tests Cohen's $D > .15$ for at least two measures in support of control; support person report Cohen's $D > .22$ in support of control). We will also explore if there are differences in effects based on level of provider training.

If data from this study suggest converting the trial into a fully-powered clinical trial, we will consider the analyses of getting the effect size as an interim analysis to inform the planning of R01, and adjust the sample size in the R01 using the method of, for instance, sample size re-estimation approach, to appropriately adjust for the alpha level for the test at the final data analysis of the full trial.

Some of the data analysis will be completed by our collaborator at Rutgers University School of Public Health. If data needs to be physically sent to our collaborator at Rutgers University School of Public Health, a DUA will be executed prior to sending.

Benefits: There are no direct benefits to subjects. This study will enable us to learn more about treatments that may help individuals with pain and active suicide ideation. Some participants may experience improvement in pain, disability, and suicide ideation.

Protected Health Information:

Privacy and Confidentiality of Data

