Social Problem-Solving Inventory-Revised (SPSI-R)⁷⁰. The SPSI-R measures problem-solving that is sensitive to change. In clinical research, the SPSI-R has been successfully used to elicit meaningful self-appraisals. The questionnaire is 52 items long. We will use the total score, as well as the 5 subscales. The

SPSI-R is internally consistent (alpha=.90) and reliable (r=.87) and has been used as an outcome of PST. Support person will also complete a version of this.

Affective Go/No Go⁷¹. This is a neuropsychological test that measures attention and impulse control. Inhibiting impulses is a key component of preventing impulsive behavior that can lead to suicide. Indeed, scores on the Go/No Go have been shown to predict suicidal behavior.

Means-End Problem-Solving Task⁷³. The MEPS is a neuropsychological test that consists of a series of scenarios, with each one identifying the beginning and end of a story. The subject's task is to come up with the middle of the story. Stories are scored according to how many steps the patient identifies in reaching the end. This instrument captures a crucial element of problem-solving: identifying the steps (i.e., means) that will lead to goal attainment (i.e., end). This aspect of problem-solving is directly relevant to patients with pain whose limited set of identified means includes suicide. An increase in effective means generated is expected to drive reduction in suicide ideation. The MEPS has been used in suicide research and has shown that suicide attempters generate fewer relevant means than both non-suicidal psychiatric controls and non-psychiatric controls.⁷⁴

Iowa Gambling Task⁷⁵. The Iowa gambling task is a neuropsychological task of problem-solving. The goal of the task is to make "money". Participants are presented with four decks of cards and have to choose cards from these decks to make "money". Subjects have the opportunity to learn about the gains and losses associated with each deck in order to maximize profit. Performance on this task has been shown to change after problem-solving therapy.⁷⁶

Emotional Stroop^{77,78}. The emotional Stroop is a test of response inhibition. This is a critical skill needed to refrain from engaging in suicidal behavior.⁷⁹ Our preliminary data suggest that Stroop is responsive to change in clinical trials for suicidal behavior.

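### The target-engagement rule draws a yes/no conclusion from point estimates of Cohen's d at 30 per arm, with no interval, no named SD and no stated baseline adjustment

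*Combined protocol and SAP*

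**What the plan says.** Specific Aims gives the purpose: "The goal of the current proposal is to ensure Problem-solving Treatment (PST) is remediating problem-solving deficits". Aim 1 is framed as estimation: "Estimate the effect of remote-delivered PST on targets". Study Population sets 30 Veterans per arm, on grounds of feasibility.

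The Data Analysis Plan computes Cohen's d within each arm and will also "calculate the effect size of the change in treatment between arms". It adds that "we will not calculate statistical significance as we are not be powered to find an effect". It then sets a decision rule: "We will conclude that our trial shows support for target engagement if we find a clinically significant effect size" in at least two of three domains. The cut-offs are d above 0.22 for self-report, above 0.15 on at least two neuropsychological tests, and above 0.22 for the support-person report. A domain that reaches its own cut-off in favour of control vetoes the pass. The next step in that section begins "If data from this study suggest converting the trial into a fully-powered clinical trial", and the rule is the only criterion stated before it.

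The plan gives no confidence interval, no SD for d, no baseline covariate and no pass probability for the rule. Involvement in Alternate Treatments promises to control for adherence and other treatments, but gives no method and no link to d. Under Primary Outcomes, the plan says of the SPSI-R: "We will use the total score, as well as the 5 subscales". It does not say which score carries a domain. Of the four neuropsychological tests, only the Means-End task has a described score.

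**The concern.** Declining to compute p-values does not remove the error rate of a rule that ends in a conclusion. At this sample size the 95% half-width of d is more than twice the largest cut-off, so a pass can easily be noise and a real effect at the cut-offs can easily be missed. Without an interval or a pass probability beside the verdict, a reader has no direct way to judge that.

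Three open choices also affect the verdict: whether the contrast is adjusted for baseline, which SD standardises it, and which score represents each measure. At stake is the answer to the trial's stated purpose, and the case for going on to a larger trial.

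**Working it through.** The plan gives no error rate or power for the rule, so there is no figure of its own to reproduce.

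**Inputs from the documents.** 30 per arm (Study Population); cut-offs 0.22 / 0.15 on at least two tests / 0.22, two of three domains, with veto (Data Analysis Plan); four neuropsychological tests (Table 2).

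**Assumptions, not in the documents.** One score per measure; a common correlation between measures of 0 to 0.5; equal pre and post SDs; a pre-post correlation r of 0.5 or 0.7. As an extreme case only, r = 0.87 on every measure, borrowed from the statement "SPSI-R is internally consistent (alpha=.90) and reliable (r=.87".

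**1. Precision.** SE(d) = sqrt(2/30) = 0.258. The half-width is 1.96 x 0.258 = 0.506. An observed 0.22 has a CI of -0.29 to 0.73; an observed 0.15 has -0.36 to 0.66.

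**2. Single domains with no effect, change SD.**
- P(d > 0.22) = 1 - Φ(0.22/0.258) = 0.197
- P(d > 0.15) = 1 - Φ(0.15/0.258) = 0.281
- At least two of four independent tests: 1 - 0.719^4 - 4 x 0.281 x 0.719^3 = 0.314

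**3. Whole rule with no effect, independent measures.** The objective domain passes without a veto with probability 0.314 - 6 x 0.281^4 = 0.277. It escapes the veto with probability 1 - 0.314 = 0.686. Self-report and support-person report are each neutral with probability 1 - 2 x 0.197 = 0.606.
- Both reports pass, objective not vetoing: 0.197^2 x 0.686 = 0.027
- One report and the objective domain pass, other report neutral: 2 x 0.197 x 0.606 x 0.277 = 0.066
- Total: 0.093

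Simulation gives 9.3% at correlation 0, 17.2% at 0.3 and 20.4% at 0.5. Participant-level simulation agrees.

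**4. Whole rule with real effects, change SD** (self-report / tests / support person).

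| True d | Passes |
|---|---|
| 0.22 / 0.15 / 0.22 | about 54% |
| 0.30 / 0.20 / 0.30 | 66-72% |
| 0.5 / 0.3 / 0.5 | 87-95% |

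Among trials that pass when the true self-report d is 0.22, the mean observed self-report d is 0.32-0.37.

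**5. Choice of SD.** Baseline-SD d = change-SD d x sqrt(2(1-r)). The factor is 1.00 at r = 0.5, 0.775 at 0.7 and 0.510 at 0.87. With the cut-offs unchanged, no-effect passes on the baseline SD are:
- r = 0.5: 9-20%
- r = 0.7: about 5.5-14.5%
- r = 0.87 on every measure (extreme case): about 1-5%

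On the same data with true effects at the cut-offs, the two SDs give different verdicts in 3-5% of trials (r = 0.5) or 10-15% (r = 0.7).

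**6. Fewer evaluable participants, change SD.** At 24 per arm, no-effect passes are about 11-23%. Support persons are optional. If only 15 per arm took part (assumed), SE = sqrt(2/15) = 0.365, the CI around 0.22 would be -0.50 to 0.94, and no-effect passes would again be 11-23%.

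**7. Baseline adjustment.** The variance of ANCOVA relative to the change contrast is (1+r)/2: 0.75 at r = 0.5 and 0.85 at r = 0.7. Thirty per arm is then worth 30/0.75 = 40 or 30/0.85 = 35 per arm with change scores.

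| r | Estimator | No-effect passes | Passes at 0.5/0.3/0.5 |
|---|---|---|---|
| 0.5 | change | 9-20% | 87-95% |
| 0.5 | ANCOVA | 8-17% | 91-97% |
| 0.7 | change | 9-20% | 88-95% |
| 0.7 | ANCOVA | 8-19% | 89-96% |

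On the same data and SD, the two estimators give different verdicts in 18-24% (r = 0.5) or 14-19% (r = 0.7) of trials at the cut-off effects. With no effect it is 9-12% or 5-10%.

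**The case against.** This is a feasibility-sized study that says openly it is not powered. Its rule is prespecified, needs two domains and carries a veto, and it claims only support. Means and SDs are planned, so a reader with the group sizes could approximate an interval. All of that is fair, but it does not put an interval or a pass probability beside the verdict. The point asks for no test and no larger sample.

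Four stronger readings are tempting, and the documents do not support them.
- *The plan has a 9-20% false-positive rate.* That range needs the change SD (or the baseline SD with r near 0.5), 30 evaluable per arm, one score per measure and assumed correlations. The plan leaves the SD open, so lower rates are equally compatible with it, and attrition would raise them.
- *The analysis is wholly unadjusted.* Control for adherence and alternate treatments is promised. What is missing is a stated baseline adjustment and a statement of how the promised control enters d.
- *The change contrast is invalid, or ANCOVA cures chance passes.* Both estimators are valid under randomisation, and ANCOVA lowers the no-effect rate only modestly. The larger disagreement figures arise at effects on the cut-offs, where a pass is close to a coin toss. Matching pairs on problem-solving may shrink the self-report gain further.
- *The d values from this rule would size the follow-on trial.* The C-SSRS entry under Exploratory Outcome names intensity of ideation as that trial's primary variable, so the sizing does not follow from these cut-offs.

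**Conclusion.** The concern holds in a conditional form. The rule turns imprecise point estimates into a conclusion, with no interval although Aim 1 is estimation, and with the SD, the baseline adjustment and the scores left open. The imprecision is firm: at 30 evaluable per arm, the CI around a just-passing 0.22 runs from about -0.29 to 0.73. The chance-pass rate is not a single number. Depending on the SD, the pre-post correlation and the number evaluable, it runs from about 5.5% to 23% over the main assumptions, and down to about 1% in the extreme case. True effects at the cut-offs would pass about 54% of the time on the change SD. All pass rates rest on assumed correlations. This should be fixed before analysis; it does not undermine the design.

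**What to change.** 1. Estimate each arm difference in the rule by ANCOVA: post-treatment score on arm and the baseline value of the same measure. State how the promised control for adherence and alternate treatments enters, for example as a sensitivity analysis.
2. Report each d with its 95% CI and number analysed, including the support-person number. State the rule's pass probability at zero and at the hypothesised effects, with the assumptions used, and describe a pass as preliminary. This step does most to answer the concern.
3. Before analysis, name one standardising SD in the units in which 0.22 and 0.15 were obtained. If the units differ, convert the cut-offs: with r = 0.7, change-SD values of 0.22 and 0.15 become 0.22 x 0.775 = 0.17 and 0.15 x 0.775 = 0.12 on the baseline SD. Without conversion, the pass rate at the cut-off effects would fall from about 54% to 42-44%. If the units cannot be established, designate one SD for the verdict and show the other as a sensitivity analysis.
4. Use the SPSI-R total for both pass and veto in the self-report and support-person domains, name one score per neuropsychological test, and report other scores descriptively.

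The cost is plan wording, one regression per measure on data already scheduled for collection, and a look-up in the team's own preliminary data. The conclusion will read more cautiously, and d may look smaller on the chosen SD.

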- **Baseline:** questionnaire packet, neuropsychological battery, and support person questionnaire packet will be collected at the start of the study (~2 hours for questionnaire packet and neuropsychological battery; ~5 minutes for the support person questionnaire packet)
- **4-week, mid treatment:** questionnaire packet will be collected after completion of the 4th session of either Problem-solving Treatment or attentional control (~30 minutes)
- **Post-treatment:** questionnaire packet, neuropsychological battery, and support person questionnaire packet will be collected after the 12th session of either Problem-solving Treatment or attentional control (~2 hours for questionnaire packet and neuropsychological battery; ~5 minutes for the support person questionnaire packet)
- **6-month follow-up assessment:** questionnaire packet will be collected ~6 months after the 12th session of either Problem-solving Treatment or attentional control (~1 hour)

See below for Table 2, which outlines when the measures and neuropsychological tests will be administered, along with a summary of each.

Table 2 – Measures administered at each timepoint

Domain	Study Instruments	Screening	Baseline	4 week	Post Treatment	6 Months
Aim 1: Primary Outcome	Social Problem-Solving Inventory Revised [SPSI-R] *		X	X	X	X
	Neuropsych Assessment: Emotional Go No-Go		X		X	
	Neuropsych Assessment: Means-End Problem-Solving Task [MEPS]		X		X	
	Neuropsych Assessment: Iowa Gambling Task		X		X	
	Neuropsych Assessment: Stroop Test		X		X	
Aim 1: Secondary Outcome	Interpersonal Needs Questionnaire [INQ]		X	X	X	X
Aim 2: Exploratory Outcome	Columbia-Suicide Severity Rating Scale [C-SSRS]	X	X		X	X
	Suicide Ideation Questionnaire [SIQ]		X	X	X	X
	Suicide-Related Coping Scale		X	X	X	X
	Pain Disability Index [PDI]		X	X	X	X
	Brief Pain Inventory [BPI]	X	X	X	X	X
Participation Characterization and Screening Instruments	Healthcare Access [HCA]		X		X	
	Demographic * / Treatment Survey	X	X		X	
	Post-Traumatic Stress Disorder Checklist [PCL]		X		X	
	The Patient Health Questionnaire-9 [PHQ-9]		X		X	X
	Patient Health Questionnaire [PHQ-15]		X		X	X
	World Health Organization Disability Assessment Schedule [WHO-DAS 2.0]		X		X	
	MOS Social Support		X		X	
	Audit-C		X		X	
	Cognitive Failures Questionnaire		X		X	X
	Coronavirus Stressor Survey	X				
Quality of Treatment Delivery	Working Alliance Inventory [WAI]			X	X	
	Patient Global Impression of Change [PGIC]				X	
	Client Satisfaction Survey				X	

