* = Veteran's support person will complete their own version

*For Veterans' who we were unable to capture the Coronavirus Stressor Survey at baseline (due to timing of its addition to the protocol), we will attempt to capture it at a follow-up timepoint (e.g. 4 week, post treatment, or 6-month follow-up assessment).

Involvement in Alternate Treatments: Throughout the course of their participation, Veterans will be allowed to begin a new treatment, continue with current medical regimen/treatments, or make changes to their existing medical regimen. For patients not currently in mental health treatment, we will communicate the availability and appropriateness of mental health services to the patient and their established provider. Adherence to medical protocols and participation in alternate treatments will be evaluated by a questionnaire during assessments and this will be controlled for in analyses.

Communication with Other Providers: In both arms, the Veteran can continue to receive care from their established providers. This includes their primary care provider and mental health provider (if they have one). If deemed clinically appropriate by a study provider, we will reach out to the Veteran's local

providers at screening to communicate the patient's active suicidal ideation. When the Veteran consents to participate in the study, the study team will send the primary care and mental health providers a letter describing the study, letting the provider know about the patient's suicidal ideation, and inviting them to contact the study team with any questions or concerns. **The letter will additionally detail that their Veteran's participation in the research study is not a replacement for standard clinical care.** During baseline, a study provider will assess suicide risk using the C-SSRS.²⁶ If the baseline C-SSRS score represents an increase from that at screening, the study provider will communicate this to the Veteran's established providers. If providers have any concern about Veteran safety at any point during their participation, a provider will reach out to the Veteran's local health care team. Additionally, providers will place a note in the electronic medical record after every session with the Veteran.

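### The plan promises to control for co-treatment without limiting this to pre-randomisation values, and does not say whether the Cohen's D in the target-engagement rule is adjusted

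*Combined protocol and SAP*

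**What the plan says.** Under Involvement in Alternate Treatments, "Veterans will be allowed to begin a new treatment, continue with current medical regimen/treatments", or alter their existing regimen, at any point in their participation. The variables to be adjusted for are "Adherence to medical protocols and participation in alternate treatments", and the instruction is that "participation in alternate treatments will be evaluated by a questionnaire during assessments and this will be controlled for in analyses". No model, covariate timing or specific analysis is named.

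Table 2 lists the "Demographic * / Treatment Survey" at screening, baseline and post-treatment, so values from after the start of treatment will be available. The baseline "questionnaire packet, neuropsychological battery, and support person questionnaire packet will be collected at the start of the study", but the protocol does not say whether that is before or after randomisation.

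The Data Analysis Plan says the team will "calculate the effect size of the change in treatment between arms", expressed as Cohen's D, and that "The analyses will be conducted with intent to treat approach". It names no covariate and plans no significance test. The decision rule reads "We will conclude that our trial shows support for target engagement if we find a clinically significant effect size for PST" over control in two of three domains. The thresholds are D above 0.22 for self-report, above 0.15 on at least two objective tests, and above 0.22 for the support person, with no domain favouring control.

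**The concern.** Treatment begun or changed after randomisation may itself be affected by the assigned arm. A between-arm difference adjusted for it is no longer the effect of being assigned to PST rather than control, which is what an intent-to-treat analysis is normally taken to estimate. If co-treatment uptake also depends on how a Veteran is faring, the adjusted difference need not equal a direct effect of PST either.

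An analyst working from the Data Analysis Plan alone would compute an unadjusted D. One who also follows the alternate-treatments section would adjust it, using post-treatment survey values if the sentence is taken literally. Both could claim to have followed the protocol. Because target engagement is declared from point estimates against fixed cut-offs, the choice can change the verdict, and nothing prevents its being made after the results are known.

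**Working it through.** **Reading the text.** The adjustment sentence closes a paragraph about treatment started or changed during participation, and refers to questionnaires given at the assessments. A baseline-only reading is possible, but nothing in the text supports it. Intent to treat fixes who is analysed and in which arm; it does not say whether D is covariate-adjusted. No other section settles the matter.

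**Could uptake differ by arm?** The Attentional control section says treatment for suicidal ideation will be recommended to patients not receiving it. The Problem-Solving Treatment section has no matching sentence. Against that, the alternate-treatments section communicates the availability of mental health services to any patient not in such treatment, in either arm. A difference is plausible but not established. Communication with Other Providers has staff contact a Veteran's providers when health or safety is a concern, so uptake may also follow prognosis.

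**Size of the shift (illustration).** The plan has no figure of its own to reproduce. From the documents: 30 per arm and the 0.22 threshold. Assumed: all uptake rates and effects. Outcomes are coded so that higher favours the patient. With uptake pC in control and pT in PST, and g the within-arm coefficient of co-treatment on outcome in SD units:

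adjusted D − unadjusted D = (pC − pT) × g

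- Equal uptake: 0 × g = 0.
- pC = 0.50, pT = 0.30, co-treatment helps and is unrelated to severity: 0.20 × 0.15 = +0.03; 0.20 × 0.30 = +0.06; 0.20 × 0.50 = +0.10.
- Same uptake, co-treatment has no effect, but severity drives uptake (odds ratio 3 per SD) and change (loading l): g = −l × (covC + covT) / [pC(1 − pC) + pT(1 − pT)], where covC and covT are the within-arm covariances of uptake with severity. Numerical integration gives covC = 0.220 and covT = 0.189, so g = −l × 0.409/0.46 = −0.89 l. The shift is 0 at l = 0, 0.20 × (−0.089) = −0.018 at l = 0.1, and −0.036 at l = 0.2. Severity that is constant over time cancels from a change score, which is why small loadings are used.
- Signs reverse if uptake is higher in PST. At 40% versus 30% the first factor halves to 0.10, and a 0.5 SD benefit gives +0.05.

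**Sampling error.** SE of D = √(2/30 + 0.22²/120) = √(0.0667 + 0.0004) = 0.26, ignoring dropout.

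**How often one threshold is crossed by one D and not the other.** Simulated trials of 30 per arm, one outcome, true unadjusted D of 0.22:

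| Assumption | Uptake 30/30 | 40/30 | 50/30 (control/PST) |
|---|---|---|---|
| No co-treatment effect, no severity link (no bias) | about 3% | about 4% | about 7% |
| Co-treatment benefit 0.3 SD | about 5% | about 7% | about 10% |
| Severity on change, l = 0.1 to 0.2, odds ratio 3 | – | – | about 7% to 8% |

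The first row is the benchmark: fitting an extra covariate in 60 people moves D across the line even when nothing is biased. Only the excess over it, 10.5% − 6.9% ≈ 4 percentage points at 50/30 with a 0.3 SD benefit, can be attributed to co-treatment affecting the outcome. Placing the true D at the threshold is the least favourable case. With a true D of 0.8, disagreement at 50/30 was 0.6% to 1.9% across the scenarios examined.

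**The case against.** The best defence is that the Data Analysis Plan is where D is defined, that it names no covariate, and that its natural reading is an unadjusted difference in change. The alternate-treatments sentence never mentions the decision rule. The trial is sized on feasibility and does no testing, and its standard error exceeds every shift shown above. All of that stands, and it limits the severity. It does not remove the ambiguity, because the sentence is an unqualified commitment about the analyses and exempts none of them. Sampling error cannot be avoided at this size, whereas this ambiguity can.

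Three stronger readings are tempting and are not supported.

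- **That the two sections flatly contradict each other.** The Data Analysis Plan is silent on covariates; it does not rule them out.
- **That control patients will take up more co-treatment, so adjustment will favour PST.** The services message covers both arms, and PST could itself raise uptake. The notice about other treatment options, in the control paragraph of Risks and Side Effects, may be a general disclosure to participants. Prognosis-driven uptake can push the shift the other way.
- **That verdicts would often flip.** Disagreement of 14% at one threshold, or 18% to 21% under the full rule, can be obtained by letting severity load 0.5 SD on the outcome. The planned D is on pre-to-post change, where stable severity cancels, so those figures do not describe this analysis.

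**Conclusion.** The concern holds as a gap in a stated rule. As written, the adjustment can cover treatment begun or changed after randomisation, and it is unclear whether it applies to the D behind the target-engagement conclusion. If it does, that D can depart from the effect of assignment.

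Neither the direction nor the size of the departure can be derived from the documents. On the assumed inputs above it is a few hundredths, at most 0.10 at 50/30 uptake, and zero in expectation if uptake is equal. Confidence is high about the gap in the text and low about any actual bias. Severity is minor to moderate.

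**What to change.** In Involvement in Alternate Treatments, end the sentence after the questionnaire assessment, delete the closing clause that promises control in the analyses, and add:

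> Adherence to medical protocols and treatments begun or changed after randomisation will be described by arm.

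In the Data Analysis Plan, add:

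> The Cohen's D used for the target-engagement rule is the between-arm difference in pre-to-post change by assigned arm, with no adjustment for adherence or for alternate treatments. Any analysis adjusting for co-treatment begun or changed after randomisation is exploratory and estimates a different quantity.

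This settles which D enters the rule and keeps co-treatment visible in the report. Excluding alternate treatments altogether from the decision-rule D also avoids depending on whether baseline precedes randomisation, which is not stated.

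The cost is two text edits and no new data. The description by arm can draw on the Treatment Survey and the medical-record treatment data already planned under Assessments. The survey's content is not shown, so whether it dates treatment changes is not known.
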